9.2 EXCLUSION CRITERIA

Any of the following criteria will exclude patients from study participation:

1. Active central nervous system tumors or metastases
2. Treatment with chemotherapy, radiation (local radiation for palliative care is permitted), hormonal anti-cancer treatment, or biologic therapy < 14 days prior to the first day of study treatment (Cycle 1 Day 1 [C1D1]).
 - b. Treatment with any other investigational agent or treatment with any anti-cancer monoclonal antibody, immunostimulant, or vaccine < 28 days prior to C1D1.
3. Any unresolved toxicity NCI CTCAE Grade ≥ 2 from previous anticancer therapy with the exception of alopecia, vitiligo, and the laboratory values defined in the inclusion criteria

- Patients with Grade ≥ 2 neuropathy will be evaluated on a case-by-case basis after consultation with the Study Physician.
- Patients with irreversible toxicity not reasonably expected to be exacerbated by treatment with durvalumab may be included only after consultation with the Study Physician.

4. History of severe allergic reactions to any of the study drug components
5. Has active or prior documented autoimmune or inflammatory disorders (including inflammatory bowel disease [eg, colitis or Crohn's disease], diverticulitis [with the exception of diverticulosis], systemic lupus erythematosus, Sarcoidosis syndrome, or Wegener syndrome [granulomatosis with polyangiitis, Graves' disease, rheumatoid arthritis, hypophysitis, uveitis, etc]). The following are exceptions to this criterion:
 - Patients with vitiligo or alopecia
 - Patients with hypothyroidism (eg, following Hashimoto syndrome) stable on hormone replacement
 - Patients with any chronic skin condition that does not require systemic therapy
 - Patients without active disease in the last 5 years may be included but only after consultation with the Moderna medical monitor
 - Patients with celiac disease controlled by diet alone.
6. Has a history of primary immunodeficiency, allogenic solid organ transplantation, or tuberculosis.
7. Immunosuppressive doses of systemic steroids or absorbed topical steroids (doses >10 mg prednisone daily equivalent) within 2 weeks before study drug administration
8. Local infection at site of a tumor lesion amenable to injection requiring anti-infective therapy within 2 weeks of the first dose of study drug
9. Receipt of live attenuated vaccine within 30 days prior to the first dose of study treatment. Note: Patients, if enrolled, should not receive live vaccine whilst receiving study treatment and up to 30 days after the last dose of study treatment.
10. History of human immunodeficiency virus infection
11. Active/chronic hepatitis B or C
12. Major surgical procedures ≤ 28 days or non-study-related minor procedures ≤ 7 days prior to C1D1. In all cases, the patient must be sufficiently recovered and stable before treatment administration.
13. Any of the following cardiac abnormalities:
 - a. Medically uncontrolled hypertension
 - b. New York Heart Association Class III or IV cardiac disease
 - c. Myocardial infarction within prior 6 months
 - d. Unstable angina
 - e. Unstable arrhythmias or mean QT interval corrected for heart rate using Fridericia's formula (QTcF) ≥ 470 ms calculated from 3 ECGs (within 15 minutes at 5 minutes apart)
14. History of another primary malignancy except for:
 - Malignancy treated with curative intent and with no known active disease ≥ 5 years before the first dose of IP and of low potential risk for recurrence

- Adequately treated non-melanoma skin cancer or lentigo maligna without evidence of disease
- Adequately treated carcinoma in situ without evidence of disease

15. Patients requiring active systemic anticoagulation at the time of intratumoral injection or biopsy

16. Active GI bleeding

17. Females who are pregnant or breastfeeding

18. Any other unstable or clinically significant concurrent medical condition (eg, substance abuse, psychiatric illness/social situations, uncontrolled intercurrent illness including active infection, arterial thrombosis, symptomatic pulmonary embolism, active interstitial lung disease, serious chronic gastrointestinal conditions associated with diarrhea, etc.) that would, in the opinion of the investigator, jeopardize the safety of a patient, impact their expected survival through the end of the study participation, and/or impact their ability to give written informed consent or comply with the protocol.

19. For patients who have received prior anti-PD-1 or anti PD-L1 therapy, a patient must not have experienced any of the following:

- a. Must not have experienced a toxicity that led to permanent discontinuation of prior immunotherapy.
- b. All AEs while receiving prior immunotherapy must have completely resolved or resolved to baseline prior to screening for this study.

20. Must not have experienced a \geq Grade 3 immune-related AE or an immune-related neurologic or ocular AE of any grade while receiving prior immunotherapy. Note: Patients with endocrine AEs of \leq Grade 2 are permitted to enroll if they are stable while maintained on appropriate replacement therapy and are asymptomatic.

21. Must not have required the use of additional immunosuppression other than corticosteroids for the management of an AE, not have experienced recurrence of an AE if re-challenged, and not currently require maintenance doses of > 10 mg prednisone or equivalent per day.

22. Has an active infection including tuberculosis (clinical evaluation that includes clinical history, physical examination and radiographic findings, and tuberculosis testing in line with local practice), hepatitis B (known positive HBV surface antigen [HBsAg] result), hepatitis C, or human immunodeficiency virus (positive HIV-1/2 antibodies). Patients with a past or resolved HBV infection (defined as the presence of hepatitis B core antibody [anti-HBc] and absence of HBsAg) are eligible. Patients positive for hepatitis C (HCV) antibody are eligible only if polymerase chain reaction is negative for HCV RNA.

23. Has a history of (non-infectious) pneumonitis that required steroids or has current pneumonitis.

24. Has a history of leptomeningeal carcinomatosis.

25. Has involvement in the planning and/or conduct of the study.

26. Must not plan to donate blood or blood components while participating in this study and through 90 days after the last dose of study treatment.

10 STUDY PROCEDURES

10.1 INTRATUMORAL INJECTIONS

Patients in the Dose Escalation period of the study must have a superficial tumor lesion amenable to injection. A tumor lesion amenable to injection during the Dose Escalation period of the study is defined as a superficial tumor lesion which is:

- Clearly visible or palpable,
- Can be easily injected without the use of imaging guidance, and
- All lesion(s) targeted for the initial injection must be ≥ 0.5 cm on longest diameter, be at least 5 mm thick, and have distinct borders based on exam or imaging, not close to critical structures such as major vessels, nerves, or airways.

Patients in the Dose Confirmation part of the study must have a visceral tumor lesion amenable to injection which is defined as:

- Visceral lesion injectable with ultrasound or computer tomography (CT) guidance
- Must not be encasing or abutting major vascular structures or are in a location that are considered high risk for AEs by the enrolling physician

Patients in the Dose Expansion part of the study must have an injectable lesion which may be either a superficial lesion or a visceral lesion which is not encasing or abutting major vascular structures or is in a location that is considered high risk for AEs by the enrolling physician.

Patients in Arm A receiving treatment to superficial lesions are to receive intratumoral injections on Day 1 and Day 15 of 28-day cycles for up to 6 cycles. All patients in Arm B and patients receiving treatment to visceral lesions are to receive intratumoral injections on Day 1 and Day 15 of 28-day cycles for Cycle 1, and on Day 1 only for Cycles 2-6.

mRNA-2416 is injected directly into the tumor. A single injection is preferred, however, the prescribed dose of mRNA-2416 may be administered as several injections into different sites within the same lesion or split across several lesions if no single lesion is large enough to receive the entire dose per the maximum injection volume per lesion size (see [Table 3](#)). All patients must have tumor(s) of sufficient size to support injection of the first planned dose of mRNA-2416. No intra-patient dose escalations may occur. If the tumor at subsequent doses has regressed or shrunk and the size of the accessible tumor burden cannot support the planned dose, then the next lowest dose supported by the tumor size may be administered following documented approval of Moderna. Lesions displaying signs of local infection should not be injected.

After insertion of the needle into the tumor it is important that the syringe plunger is gently withdrawn a short distance to ensure that the needle tip is within tumor parenchyma and not in a blood vessel. There is no safety data to support administration of mRNA-2416 directly into a vein or artery. Formal toxicology studies have deployed subcutaneous dosing in rats and non-human primates. If mRNA-2416 appears to extravasate from the tumor injection site into surrounding subcutaneous tissue patients should be followed for adverse reactions according to the protocol but no additional immediate action needs to be taken.

For patients receiving mRNA-2416 in combination with durvalumab, the ITu injection of mRNA-2416 should be administered first with at least a 30 minute break between the two study treatments.

Table 3: Maximum Injection Volume per Lesion Size

Lesion Size (Longest Dimension)	Injection Volume
≤ 0.5 cm	up to 0.1 mL
>0.5 cm to 1.5 cm	up to 0.5 mL
>1.5 cm to 2.5 cm	up to 1.0 mL
>2.5 cm to 5 cm	up to 2.0 mL
>5 cm	up to 4.0 mL

Each patient should be carefully monitored for possible injection related reactions. It is recommended that investigators observe all patients for a minimum of 1 hour after administration of each mRNA-2416 injection, with continuous monitoring of pulse oximetry and vital sign assessment every 10 minutes for the first 30 minutes followed by every 15 minutes for the first hour. If an injection related reaction occurs, patients should be treated symptomatically as per standard of care and the Moderna Medical Monitor should be notified. Additionally, blood samples for complement activation of tryptase within 2 hours of the reaction are requested if feasible. The patient should be instructed to call the clinical site if any such reactions develop or don't resolve within 24 to 48 hours. All reactions will be recorded as an adverse event.

10.2 DURVALUMAB ADMINISTRATION

Durvalumab will be supplied by the Sponsor as a 500-mg vial solution for infusion after dilution. The solution contains 50 mg/mL durvalumab, 26 mM histidine/histidine-hydrochloride, 275 mM trehalose dihydrate, and 0.02% weight/volume (w/v) polysorbate 80; it has a pH of 6.0 and density of 1.054 g/mL. The nominal fill volume is 10.0 mL. Investigational product vials are to be stored at 2°C to 8°C (36°F to 46°F) and must not be frozen. Drug product should be kept in original packaging until use to prevent prolonged light exposure.

Preparation of durvalumab doses for administration with an IV bag

The dose of durvalumab for administration must be prepared by the investigator's or site's designated investigational product (IP) manager using aseptic technique. Total time from needle puncture of the durvalumab vial to the start of administration should not exceed the following:

- 24 hours at 2°C to 8°C (36°F to 46°F)
- 4 hours at room temperature

A dose of 1500 mg (for patients > 30 kg in weight) will be administered using an IV bag containing 0.9% (w/v) saline or 5% (w/v) dextrose, with a final durvalumab concentration ranging from 1 to 15 mg/mL, and delivered through an IV administration set with a 0.2- or 0.22- μ m filter. Add 30.0 mL of durvalumab (ie, 1500 mg of durvalumab) to the IV bag. The IV bag size should be selected such that the final concentration is within 1 to 15 mg/mL. Mix the bag by gently inverting to ensure homogeneity of the dose in the bag.

If a patient's weight falls to \leq 30 kg, weight-based dosing at 20 mg/kg will be administered using an IV bag containing 0.9% (w/v) saline or 5% (w/v) dextrose, with a final durvalumab concentration ranging from 1 to 15 mg/mL, and delivered through an IV administration set with a 0.2- or 0.22- μ m filter.

Standard infusion time is 1 hour; however, if there are interruptions during infusion, the total allowed infusion time should not exceed 8 hours at room temperature.

Do not co-administer other drugs through the same infusion line.

The IV line will be flushed with a volume of IV diluent equal to the priming volume of the infusion set used after the contents of the IV bag are fully administered, or complete the infusion according to institutional policy to ensure the full dose is administered.

If either preparation time or infusion time exceeds the time limits a new dose must be prepared from new vials. Durvalumab does not contain preservatives, and any unused portion must be discarded.

Vital Sign Monitoring

Vital signs (blood pressure [BP], pulse, temperature, and respiration rate) will be evaluated according to the Schedule of Events. Body weight is also recorded at each visit along with vital signs.

First infusion

On the first infusion day, patients will be monitored and vital signs collected/recorded in eCRF prior to, during, and after infusion of IP as presented in the bulleted list below.

BP and pulse will be collected from patients in the IO arms before, during, and after each infusion at the following times (based on a 60-minute infusion):

- Prior to the beginning of the infusion (measured once from approximately 30 minutes before up to 0 minutes [ie, the beginning of the infusion])
- Approximately 30 minutes during the infusion (halfway through infusion)
- At the end of the infusion (approximately 60 minutes \pm 5 minutes)

If the infusion takes longer than 60 minutes, then BP and pulse measurements should follow the principles as described above or be taken more frequently if clinically indicated. A 1-hour observation period is recommended after the first infusion of durvalumab.

Subsequent infusions

BP, pulse, and other vital signs should be measured, collected/recorded in eCRF prior to the start of the infusion. Patients should be carefully monitored and BP and other vital signs should be measured during and post infusion as per institution standard and as clinically indicated. Any clinically significant changes in vital signs should be entered onto an unscheduled vital signs CRF page

10.3 mRNA-2416 DOSE MODIFICATION

Patients who experience study treatment-related toxicity that leads to a dose interruption, following recovery to at least Grade 1 or to baseline, continue to receive injections at 50% of the planned dose based on investigator discretion. Patients may not be rechallenged at the planned dose.

Patients with a lesion that has become inaccessible or has decreased in tumor volume during the study treatment period, such that the planned dose is no longer able to be administered, may continue with study therapy at a lower dose following documented approval from Moderna.

For patients who do not tolerate the protocol-specified dosing schedule of mRNA-2416, dose reductions may be permitted in order to allow the patient to continue study therapy. If a patient experiences an AE meeting the criteria for DLT as defined in [Section 8.4.2](#), study therapy should be withheld. Following resolution of the toxicity to grade 1 or to the patient's baseline value, the patient may resume study therapy at 50% of the planned dose.

10.4 DURVALUMAB DOSE MODIFICATION AND TOXICITY MANAGEMENT GUIDELINES

Dose delays are permitted for durvalumab (please see Appendix E for dose modification and toxicity management guidelines), however dose reductions are not permitted for durvalumab.

10.5 Dose Omissions and Discontinuation of Study Drug Administration

Study treatment may be interrupted for situations other than treatment-related AEs such as medical and/or surgical events or logistical reasons not related to study treatment. Patients should be placed back on study

treatment within 3 weeks of the scheduled interruption, unless otherwise discussed with the Sponsor. The reason for interruption should be documented in the patient's study record.

Patients who have permanently discontinued study therapy will be scheduled for an End of Treatment visit within 14 days (± 2 days) of the decision to permanently discontinue study therapy and assessments will be performed per the Schedule of Events table ([Section 3](#)). Patients who have permanently discontinued study therapy should not be considered withdrawn from the study. They should return for the 30-day and 90-day safety follow-up visit from last dose and the tumor assessment follow-up visits per the Schedule of Events table. If the patient fails to return for these assessments for unknown reasons, every effort (e.g. telephone, email, letter) should be made to contact them.

The following are reasons for discontinuing study therapy without necessarily requiring withdrawal from the study:

- Patients who have completed 6 cycles of study therapy and have an overall tumor assessment of SD or better
- Patients who have experienced a Grade 4 treatment-related AE at any time during study treatment must discontinue from study treatment
- Patients who, in the opinion of the investigator, have incurred a Grade 3 drug-related DLT that has not recovered to Grade 1 or less within 14 days, or has recurred following restarting study therapy at a modified dose level.
- Patients who, in the opinion of the investigator, have incurred unacceptable toxicity that does not meet the pre-determined criteria for DLT (eg, late-onset, treatment-emergent toxicity after the DLT assessment window, or Grade 2 toxicities that are sufficiently durable or unresponsive to supportive intervention as to render them unacceptable in the opinion of the investigator) which has not recovered to Grade 1 or less within 28 days, or has recurred following restarting study therapy at a modified dose level.
- Patients who experience a Grade 3 hypersensitivity reaction or autoimmune events must discontinue from study treatment
- Patients who no longer have lesions that meet criteria for injection
- Pregnancy
- Physician's decision
- Patient/guardian decision
- Patients will be withdrawn from study due to progressive disease per irRC/LYRIC. Due to the possibility of pseudoprogression; patients should not be withdrawn from the study due to progressive disease per RECIST v1.1 or Cheson 2014 criteria.
- Patient has received alternative anti-cancer therapy
- Patient has symptomatic progression of disease, or other clinical conditions which, in the opinion of the investigator, render it in the interests of the patient to withdraw from the study.

The reason for discontinuation of study therapy should be recorded on the appropriate page(s) of the electronic case report form (eCRF).

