8.4.2 DEFINITION OF DOSE-LIMITING TOXICITIES

A dose-limiting toxicity (DLT) is defined as an adverse event or abnormal laboratory value assessed as unrelated to disease, disease progression, inter-current illness, or concomitant medications and at least possibly related to the study therapy and that occurs within the first 28 days of study therapy. The investigator must notify the Sponsor immediately of any DLTs.

For patients in Arm A receiving mRNA-2416, the following toxicities will be considered a DLT:

- All Grade 3 AEs with the exception of the following:
 - Grade 3 thrombocytopenia lasting <7 days
 - Grade 3 neutropenia without fever or lasting <7 days
- Any Grade 4 or Grade 5 toxicity. Death due to disease progression is not considered a DLT.

For patients in Arm B receiving mRNA-2416 in combination with durvalumab, the following toxicities will be considered a DLT:

Adverse Event (AE)+C2:F16	DLT Criteria		
	Grade 2 Events	Grade 3 Events	Grade 4 events
Diarrhea/colitis	none	Events that do not resolve to Grade 1 or baseline within 14 d (whether or not it is immune-mediated)	DLT
Pneumonitis	Non-infectious pneumonitis that does not resolve to Grade ≤1 within 10 days	Non-infectious pneumonitis is a DLT	DLT
Hepatitis	none	Alanine aminotransferase (ALT) or aspartate aminotransferase (AST) >8×ULN or total bilirubin (TBL) >5×ULN OR events meeting Hy's Law (AST or ALT ≥3×ULN with concurrent increase in TBL ≥2×ULN without evidence of cholestasis or alternative explanations)	DLT
Rash	Any grade rash with bullous formation.	Rash not resolving to Grade 1 or baseline within 30d. Any rash with bullous formation.	DLT
Peripheral neuromotor syndromes such as Guillain-Barre or myasthenia gravis	Events not resolving to Grade 1 within 30d. Events with any signs of respiratory insufficiency or autonomic instability.	Events that do not resolve to Grade 1 within 30d. Events with any signs of respiratory insufficiency or autonomic instability.	DLT
Myocarditis	Events that do not resolve to Grade 1 within 3d OR a biopsy confirms immune-mediated myocarditis.	All Grade 3 myocarditis.	DLT
Myositis/polymyositis	Events that do not resolve to Grade 1 within 30d OR exhibit signs of respiratory insufficiency regardless of optimal medical management	Events that do not resolve to Grade 1 within 30d OR exhibit signs of respiratory insufficiency regardless of optimal medical management	DLT

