Endocrinopathies involving thyroid or pituitary glands or adrenal insufficiency	none	Excludes events that are managed with or without systemic corticosteroid therapy and/or hormone replacement therapy and the patient is asymptomatic	
Type I diabetes mellitus	none	Events that are not managed with appropriate diabetic therapy	
Nephritis	none	Any immune-mediated increase in creatinine >3×ULN, or >3×baseline for patients with a baseline creatinine elevated above ULN	DLT
Elevated amylase or lipase/pancreatitis	none	Elevations in amylase or lipase >2.0×ULN with signs or symptoms of pancreatic inflammation	
All other imAEs OR non-imAEs	none	Events that do not resolve to Grade 1 or baseline within 30d	DLT
Infusion-related reactions	none	Events that do not resolve within 6h despite appropriate medical management.	DLT

- Any Grade ≥ 3 immune or non-immune adverse event (AE) that is at least possibly related to the investigational product (IP) or investigational regimen (IR) with two exceptions: Any grade of vitiligo or alopecia
- Hematologic toxicity:
 - Grade ≥ 3 neutropenia complicated by fever $>38.3^{\circ}\text{C}$
 - Grade 4 neutropenia (lasting more than 7 days)
 - Grade ≥ 3 thrombocytopenia with significant bleeding
 - Grade 4 thrombocytopenia (regardless of duration)
 - Grade 4 anemia (regardless of duration)

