- For persistent (> 3 to 5 days) low-grade (Grade 2) or severe (Grade ≥ 3) events, promptly start prednisone 1 to 2 mg/kg/day PO or IV equivalent.
- Some events with high likelihood for morbidity and/or mortality – eg, myocarditis, or other similar events even if they are not currently noted in the guidelines – should progress rapidly to high dose IV corticosteroids (methylprednisolone at 2 to 4 mg/kg/day) even if the event is Grade 2, and if clinical suspicion is high and/or there has been clinical confirmation. Consider, as necessary, discussing with the Study Physician, and promptly pursue specialist consultation.
- If symptoms recur or worsen during corticosteroid tapering (28 days of taper), increase the corticosteroid dose (prednisone dose [eg, up to 2 to 4 mg/kg/day PO or IV equivalent]) until stabilization or improvement of symptoms, then resume corticosteroid tapering at a slower rate (> 28 days of taper).
- More potent immunosuppressives such as TNF inhibitors (eg, infliximab) (also refer to the individual sections of the imAEs for specific type of immunosuppressive) should be considered for events not responding to systemic steroids. Progression to use of more potent immunosuppressives should proceed more rapidly in events with high likelihood for morbidity and/or mortality – eg, myocarditis, or other similar events even if they are not currently noted in the guidelines – when these events are not responding to systemic steroids.
- With long-term steroid and other immunosuppressive use, consider need for *Pneumocystis jirovecii* pneumonia (PJP,

General considerations

Dose modifications

drug/study regimen should be permanently discontinued in Grade 2 events with high likelihood for morbidity and/or mortality – eg, myocarditis, or other similar events even if they are not currently noted in the guidelines – when they do not rapidly improve to Grade < 1 upon treatment with systemic steroids and following full taper

Note: There are some exceptions to permanent discontinuation of study drug for Grade 4 events (ie, hyperthyroidism, hypothyroidism, Type 1 diabetes mellitus).

Toxicity management

formerly known as *Pneumocystis carinii* pneumonia) prophylaxis, gastrointestinal protection, and glucose monitoring.

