Adverse Events	Severity grade of the Event (NCI CTCAE version 4.03)	Dose modifications	Toxicity management
Gravis and Guillain- Barre)	the grade/severity)	CTC	
Monitor patient for general symptoms (headache, nausea, vertigo, behavior change, or weakness).Consider appropriate diagnostic testing (eg, electromyogram and nerve conduction investigations).Perform symptomatic treatment with neurological consult as appropriate.
Grade 1	No dose modifications.	For Grade 1:	
See “Any Grade” recommendations above.
Grade 2	For acute motor neuropathies or neurotoxicity, hold study drug/study regimen dose until resolution to Grade ≤ 1 . For sensory neuropathy/neuropathic pain, consider holding study drug/study regimen dose	For Grade 2:	
Consider, as necessary, discussing with the Study Physician.Obtain neurology consult.Sensory neuropathy/neuropathic pain may be managed by appropriate medications (eg, gabapentin or duloxetine).

Specific immune-mediated reactions

Adverse Events	Severity grade of the Event (NCI CTCAE version 4.03)	Dose modifications	Toxicity management
		
until resolution to Grade \leq 1.
 
If toxicity worsens, then treat as Grade 3 or 4.
 
Study drug/study regimen can be resumed once event improves to Grade \leq 1 and after completion of steroid taper.
	
- Promptly start systemic steroids prednisone 1 to 2 mg/kg/day PO or IV equivalent.- If no improvement within 3 to 5 days despite 1 to 2 mg/kg/day prednisone PO or IV equivalent, consider additional workup and promptly treat with additional immunosuppressive therapy (eg, IV IG).
Grade 3 or 4	For Grade 3:	
Hold study drug/study regimen dose until resolution to Grade \leq 1.
 
Permanently discontinue study drug/study regimen if Grade 3 imAE does not resolve to Grade \leq 1 within 30 days.
	
For Grade 3 or 4:
 
- Consider, as necessary, discussing with Study Physician.- Obtain neurology consult.- Consider hospitalization.- Promptly initiate empiric IV methylprednisolone 1 to 2 mg/kg/day or equivalent.- If no improvement within 3 to 5 days despite IV corticosteroids, consider additional workup and

Specific immune-mediated reactions

Adverse Events	Severity grade of the Event (NCI CTCAE version 4.03)	Dose modifications	Toxicity management

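### Section 10.5 requires stopping after any related Grade 4 event and after Grade 3 autoimmune events, but Appendix E (mainly Arm B) and Section 10.3 (both arms) allow retreatment for some of the same events, and no text says which governs

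*Protocol*

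**What the plan says.** **Section 10.5** lists reasons for ending study therapy. Two are absolute. For Grade 4: "Patients who have experienced a Grade 4 treatment-related AE at any time during study treatment must discontinue from study treatment". For Grade 3: "Patients who experience a Grade 3 hypersensitivity reaction or autoimmune events must discontinue from study treatment". A third applies where a Grade 3 drug-related DLT has not returned to Grade 1 or less in 14 days. A fourth covers unacceptable toxicity outside the DLT criteria and allows 28 days.

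**Appendix E** reaches the plan through Section 10.4, on durvalumab. Section 12.1.5 says it covers events judged causally related to the study drug and/or regimen. Its general section states: "There are some exceptions to permanent discontinuation of study drug for Grade 4 events", naming hyperthyroidism, hypothyroidism and Type 1 diabetes. Elsewhere it:

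- lets other Grade 3 or 4 endocrinopathies be held and retreated once stable and after the steroid taper;
- does not mandate stopping for Grade 3 or 4 inflammatory reactions attributed to local tumor response;
- leaves Grade 4 laboratory events to clinical judgement and consultation with the Sponsor;
- provides for hold and resumption after Grade 3 colitis, rash, neurotoxicity, neuromotor syndromes and myositis. For neurotoxicity the wording is "Permanently discontinue study drug/study regimen if Grade 3 imAE does not resolve to Grade" 1 or less within 30 days;
- directs resumption after Grade 3 hepatitis with lower elevations that recovers within 14 days, once the taper is complete.

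**Section 10.3**, headed for mRNA-2416, withholds therapy after an event meeting the DLT criteria. After resolution to Grade 1 or baseline, "the patient may resume study therapy at 50% of the planned dose". It sets no upper grade and no time limit.

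**Section 8.4.2** counts "Any Grade 4 or Grade 5 toxicity" as a DLT in Arm A. For Arm B it gives an event-by-event table and, separately, a bullet covering every related event of Grade 3 or higher except vitiligo and alopecia.

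**The concern.** Three sections answer the same question, whether this patient may be treated again, and for some events they answer it differently. The first stake is patient safety: two patients with the same event could be stopped at one site and retreated at another, each in line with some part of the protocol.

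The second stake is reporting. The SAP tabulates reasons for discontinuing each drug (Section 5.1), dose modifications and actions taken (Section 7.3.4), and TEAEs leading to discontinuation of each drug (Section 9.1). Where the stopping rule is ambiguous, those tables reflect both tolerability and the section each site followed, and the two cannot be separated afterwards.

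**Working it through.** No arithmetic applies. The check sets Sections 8.4.2, 10.3, 10.4, 10.5 and Appendix E side by side for specific cases and looks for a clause that ranks them.

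**Step 1: do 10.3 and 10.5 cover the same events?** A DLT under 8.4.2 must be at least possibly related to study therapy, and Section 12.3 has possibly related events recorded as related. A Grade 4 DLT is therefore also a Grade 4 treatment-related event under 10.5. The two sections overlap in both arms.

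**Step 2: do Appendix E and 10.5 cover the same events?** Appendix E applies to events related to the study drug and/or regimen. Section 10.5 is not restricted by arm or drug. They overlap in Arm B.

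**Step 3: apply the rules case by case.**

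| Case | Section 10.5 | Other text |
|---|---|---|
| a. Either arm: related Grade 4 event in the first 28 days, resolved to Grade 1 | must stop | 10.3: may resume at 50% |
| b. Arm B: related Grade 4 adrenal insufficiency, stabilised | must stop | Appendix E: can be retreated after the taper |
| c. Arm B: related Grade 4 laboratory abnormality | must stop | Appendix E: clinical judgement |
| d. Arm B: Grade 3 immune-mediated hepatitis, lower elevations, recovered on day 10 | must stop, if it counts as autoimmune | Appendix E: directs resumption after the taper |

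The outcomes differ in all four. Case d depends on the word *autoimmune*, which 10.5 does not define. Appendix E itself describes thyroiditis, pancreatitis and hypophysitis as possibly autoimmune, so the two vocabularies are not cleanly separate.

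**Step 4: the recovery window.** Take an Arm B Grade 3 rash without bullae that recovers on day 20.

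- By the Arm B table in 8.4.2, such a rash is a DLT only if it has not resolved within 30 days. This one is not a DLT, so the 14-day limit does not apply. Day 20 also lies within the 28 days allowed for non-DLT toxicity.
- By the separate Grade 3 or higher bullet, it is a DLT. Day 20 exceeds 14 days, so 10.5 makes it a reason to stop, while Appendix E's 30-day window is still open.

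The 14-versus-30-day conflict therefore exists only under the second definition. The same holds for the other Grade 3 events with a 30-day window in Appendix E: neurotoxicity, neuromotor syndromes and myositis.

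**Step 5: precedence.** No clause in 10.3, 10.4, 10.5, 12.1.5 or Appendix E ranks the sections. Section 10.7 cites 10.3 and Appendix E together without ranking them.

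**The case against.** The strongest reply is that most of the retreatment text is permissive. Section 10.3 says a patient may resume, and much of Appendix E says treatment can be resumed. Appendix E is framed as recommended guidance, and Section 12.1.5 describes it as an aid to the investigator's clinical judgement. A specific instruction to stop can be read as limiting a general permission. This largely stands: a site that always took the strictest rule would often breach nothing. But no text tells sites to read it that way, and the hepatitis entry is an instruction rather than a permission.

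Three stronger readings might be inferred, and the documents do not support them.

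- *Sites cannot comply with all the rules.* This is literal only where Appendix E directs and 10.5 forbids. Elsewhere the sections agree: Appendix E also requires stopping for Grade 3 or 4 pneumonitis, nephritis and infusion-related reactions. Section 10.5 itself foresees restarting at a modified dose level, so a non-autoimmune Grade 3 DLT that recovers within 14 days fits both 10.3 and 10.5.
- *The 50% restart contradicts the ban on durvalumab reductions.* Section 10.4 does say "however dose reductions are not permitted for durvalumab". But 10.3 is headed for mRNA-2416 and speaks of injections, so the headings largely settle which drug each rule covers. What remains is the loose term *study therapy* in 10.3.
- *The response results are compromised.* Section 10.5 keeps patients who stop therapy in the study and asks them to return for tumor assessment visits. No effect on the response rate is shown.

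**Conclusion.** The concern holds in this form. There are two firm contradictions in current text: 10.5 against Appendix E on Grade 4 and Grade 3 autoimmune events, mainly in Arm B, and 10.5 against 10.3 on Grade 4 DLTs, in both arms. Two points are secondary: the 14-day and 30-day windows, which conflict only under one of the two Arm B DLT definitions, and the scope of *study therapy* in 10.3.

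The size is qualitative. The documents give no expected frequency for these events, so the number of patients affected cannot be derived. The Grade 4 conflicts rest on the wording alone. The Grade 3 hepatitis conflict also assumes that immune-mediated hepatitis is an autoimmune event under 10.5. No view is taken on which clinical rule is right.

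**What to change.** In one amendment, reconcile Sections 10.3, 10.5 and Appendix E:

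- State which section governs for each arm and each drug, and remove the conflicting statements elsewhere.
- Say whether the events that Appendix E calls immune-mediated are autoimmune events for 10.5.
- Say whether the 10.3 restart provision covers Grade 4 DLTs.
- Reconcile the Arm B table and the Grade 3 or higher bullet in 8.4.2, because they set the reach of the 14-day rule.
- Word 10.3 by drug, so that it matches its own heading and Section 10.4.

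The sponsor decides the clinical content. The cost is amendment wording and its approval. Sample size, endpoints and SAP methods do not change.
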